This design poses minimal risk to participants. All individuals included have previously consented to receive virtual communications—including appointment reminders and provider messages—from Centretown Community Health Centre (CCHC). The reminder used in this study aligns with these routine communications and does not introduce undue influence or burden.

Debriefing will be provided to all participants after the observation period, either in person (if attending a DRS appointment) or via email (if they do not attend). This post-trial communication satisfies TCPS 2 requirements for appropriate safeguards when consent is waived.

Overall, the waiver is justified on methodological, ethical, and practical grounds, with a favourable balance of potential benefits to risks.

Consent / Assent and Other Informational Documents Provided to Participants

Debriefing forms describing in detail the study intervention/observations, study procedures, and risks are given to the participant and is submitted with this protocol:

Debriefing Form

- Participants who attend a DRS appointment during the active intervention period will be debriefed in person by CCHC staff before screening. They will receive the debriefing form and have the opportunity to ask questions or withdraw from the study at that time.
- Participants who do not attend a DRS appointment will be debriefed in writing. The debriefing form will be sent via the OCEAN EMR using the same method as the reminder distribution.
- CCHC staff will document debriefing in each participant's EMR and record any withdrawal requests accordingly.

Research Data Management

Data Management Plan

The following OHRI researchers will have access to the data JP (Principal Investigator), MD, EG, JO. The primary contact/ person responsible for answering any questions about or managing access to the data is [name].

Type of Data	Purpose	Data	Data Storage	Accessible
		Capture		by
		Systems		
De-identified clinical and	To describe sample and	Electronic	Once exported	JP. JO,
appointment attendance data	observe patterns in	Medical	from the EMR into	MD. EG.
including variables from the	appointment attendance	Record at	Excel by the data	MT. BY
in-chart trial tracker:	by sociodemographic	CCHC	manager at the	
intervention condition, date	variables and to answer		CCHC, file will	
of contact, type of contact,	research question of		locked for changes	
appointment booked,	attendance to DRS per		and be shared to a	
interpretation booked,	arm.		secure SharePoint	
appointment attended,			file between OHRI	
retinopathy detected, spoken			and CCHC.	
language, age, FSA, prior DRS				
attendance.				
Web analytics (basic metrics	To describe website use	Google	Data will be	JP. JO,
including number of website	as this is the platform for	analytics or	exported to a	MD. EG
visits, duration of website	the intervention.	website	secure SharePoint	
visit/ session. clicks on		developer	by the Site Owner	
secondary link) No web		analytics	(CCHC)	
identifiers (e.g., IP address				
are to be collected)				

Data Collection and Management Responsibilities

De-identified quantitative data will be collected as part of the reminder evaluation. Only the variables specified in the Reminder Trial Tracker will be collected. Final data collection at the site level may continue beyond the active intervention period to allow documentation of any appointments or withdrawal requests that occur before participants are debriefed. This data will be stored in CSV format on a secure OHRI SharePoint site with access limited to study team members responsible for the analysis.

Data Sharing and Reuse

Identifiable data will not be shared. Summaries of analysed data may be shared with relevant partners (i.e., CCHC, Diabetes Action Canada, OHRI research team meetings) prior to the submission of final reports or manuscripts.

De-identified and cleaned datasets, with all direct and indirect identifiers removed, may be uploaded to a secure open-access repository such as the Federated Research Data Repository (FRDR). FRDR is a national platform designed to support the sharing and preservation of Canadian research data.

Study Records Retention

Raw data, data summaries and analyzed data will be stored in a secure file within SharePoint that can only be accessed restricted to members of the study team. Should a researcher leave before the end of the data retention (i.e., 10 years post study completion), they will be removed from the shared folder. JP is responsible for any questions during the retention period.

Protocol Deviations

Any need to deviate from the approved protocol will be reported to the REB and no changes will be made to the approved protocol without informing the REB.

Knowledge Translation

Knowledge Translation (KT) will be integrated throughout the research process. The KT plan will evolve as the study progresses (Barwick, 2022). Early in the project, knowledges users (KUs) will be engaged to provide feedback on the research plan, particularly on outreach and reminder development drawing on their lived experiences. KUs will be consulted again after data collection, to co-develop and review KT strategies and products.

Before participating, all KUs will be fully informed about expectations of collaborators, available participation options, and levels of commitment. The research team will strive to ensure that collaboration is accessible, flexible, and low risk.

The final KT product is not yet determined but will include:

- a) development and dissemination of tailored key messages;
- b) implementation strategies to promote changes in practice (e.g., improved appointment attendance and outreach); and
- c) an evaluation of the KT plan and product for comprehensiveness, alignment, and feasibility (Barwick, 2019).

A potential KT product is a multilingual guide for clinical KUs outlining effective strategies to improve attendance for recommended screening (e.g., annual DRS. This guide would address sociodemographic and structural barriers, include quotes from KUs, and infographics and other accessible materials. It may take the form of online or hardcopy resources, such as a fillable multilingual outreach template. Once finalised, appropriate resources will be allocated for its development.

KT will be appraised using Barwick's evaluation criteria (Barwick, 2019). Findings will also be submitted for publication in open access, peer-reviewed journals with high impact.

References

- 2. Cheng AYY. Clinical Practice Guidelines. *Canadian Journal of Diabetes*. 2013;37:S1-S3. doi:10.1016/j.jcjd.2013.01.009
- 3. Agence de santé publique du Canada. Fardeau économique de la maladie au Canada, 2010.; 2018. Accessed February 24, 2020. http://epe.lac-bac.gc.ca/100/201/301/weekly_acquisitions_list-ef/2018/18-31/publications.gc.ca/collections/collection_2018/aspc-phac/HP45-21-2018-fra.pdf
- Cruess AF, Gordon KD, Bellan L, Mitchell S, Pezzullo ML. The cost of vision loss in Canada.
 Results. Canadian Journal of Ophthalmology / Journal Canadien d'Ophtalmologie.
 2011;46(4):315-318. doi:10.1016/j.jcjo.2011.06.006

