increase DRS	regularly have their eyes	at CCHC.	observation
attendance in	screened.		period.
participants living			
with diabetes,			
compared to not			
sending a			
reminder.			

Secondary Objectives

Objective Brief Description/Justification o Outcome Measure		Outcome Measured By	Time Frame
Assess whether linguistically tailored reminders incorporating BCTs increase DRS appointment bookings in participants living with diabetes, compared to not sending a reminder.	Not all participants who book an appointment may attend an appointment. Assessing appointment booking in addition to appointment attendance is important to understand if the intervention is effective in both promoting appointment booking and attendance.	The proportion of participants in each condition who book a DRS appointment at CCHC.	Assessed at the conclusion of the intervention/ observation period.
To examine whether the effect of the intervention on DRS attendance is moderated by participant characteristics, including age, gender/sex, preferred language, prior DRS attendance, and Forward Sortation Area (FSA).	Participant characteristics are likely to influence appointment booking and attendance.	Interaction effects between intervention group and subgroup variables (age, gender/sex, preferred language, prior DRS attendance, FSA) in a logistic regression model predicting DRS attendance.	Assessed at the conclusion of the active intervention period (4 months after first wave of reminders is sent).

Study Design and Endpoints

Description of Study Design

This study is a two-arm randomized controlled trial (RCT) evaluating the effectiveness of a linguistically tailored, BCT based electronic reminder in promoting diabetic retinopathy screening (DRS) attendance. Participants will be randomly assigned to one of two study arms:

- Control group (no reminder)
- Reminder Group (receives reminder incorporating knowledge, social and goal based BCTS).

Participants will be drawn from the Community Diabetes Education Program of Ottawa (CDEPO), registered at Centretown Community Health Centre (CCHC). To avoid overloading clinic resources, reminders will be sent in two waves. Control group participants will be matched to these waves based on distribution timing.

Duration of Study Participation

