The study is expected to last approximately 120 days from the start of the intervention to the completion of the active intervention period for participants in wave 2. Final data collection will continue until all participants have been debriefed to ensure accurate documentation of participation status and any withdrawal requests.

Participants' time commitment will vary based on their study condition and actions taken. Estimates of individual participation time by assigned condition and action taken are presented in the table below:

Group	Action taken	Read	Book	Attend	Receive	Total
		reminder	appointment	appointment	debrief	time
Control group	Do not book or attend an	-	-	-	5 mins	5 mins
	appointment					
	Book, but do not attend	-	20 mins	-	5 mins	25
	appointment					mins
	Book & attend	-	20 mins	60 mins	5 mins	85
	appointment					mins
Intervention	Do not book or attend an	5 mins	-	-	5 mins	10
group	appointment					mins
	Book, but do not attend	5 mins	20 mins	-	5 mins	30
	appointment					mins
	Book & attend	5 mins	20 mins	60 mins	5 mins	90
	appointment					mins

Total Number of Participants and Sites

This is a single-site study conducted at Centretown Community Health Centre (CCHC). The study will include a randomly selected subsample (N = 330) of eligible individuals listed in the Community Diabetes Education Program of Ottawa (CDEPO) patient database at CCHC. Participants will be randomly allocated 1:1 to either an intervention or control arm (165 per arm). To support clinic capacity, intervention participants will receive reminders in two waves. Control participants will be matched to these waves to ensure comparable observation periods. This sample size achieves 80% power to detect a 10% difference in the primary outcome of screening attendance between the groups (or a proportion of 0.03 in the control arm versus 0.13 in the intervention arm), using a two-sided Z-test with pooled variance at a 5% significance level. Some attrition is anticipated due to outdated contact details or death; thus, our calculation accounts for approximately 10% attrition.

Study Enrollment and Withdrawal

Eligible participants listed on the CDEPO database (i.e., clients with existing medical charts in the CCHC's Electronic Medical Records (EMR), housed on PS Suite v. A-5.24.204, a certified EMR system

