hosted by TELUS Health Solutions Inc.) will be identified by CCHC staff. Three hundred and thirty of those eligible will be randomly selected to participate in the study and automatically enrolled.

Participant Inclusion Criteria

Individuals are eligible to participate in the study if they:

- a) Are registered to the CDEPO program at CCHC, and
- b) have T1DM or T2DM, and
- c) have consented to virtual communications from CCHC (as indicated by the inclusion of their email address in the CCHC EMR), and
- d) are 18 years of age or older
- e) have an active chart (i.e., chart has been updated within the last two years, and
- f) have not already attended a DRS appointment with DESO (as indicated in the individual's EMR).

Participant Exclusion Criteria

Individuals are ineligible to participate in this study if they:

- a) Are not registered to the CDEPO program at CCHC, or
- b) are registered in CDEPO at CCHC but do not:
 - o have T1DM or T2DM, or
 - have not consented to virtual communications from CCHC (as indicated by an email address not being listed in the client's EMR), or
 - o are not 18 years of age or older
 - o Do not have a chart that has a been active in the last two years, or
 - have already attended a DR screening appointment with DESO (as indicated in chart).

Strategies for Recruitment and Retention

As contacting participants in advance would introduce bias, consent for trial participation will be waived. Participants will be debriefed after the trial concludes, either in person or by email, depending on their engagement with the DRS appointment process. Those who attend a DRS appointment will be debriefed in person at CCHC in the eye screening room upon arrival. Those who do not attend will receive a post-study debrief via email, using the OCEAN platform.

Given the passive nature of participation—limited to receiving a reminder and the option to attend a routine DRS appointment—no additional recruitment or retention strategies are necessary.

Participant Withdrawal or Termination

Reasons for Withdrawal or Termination

Participants are free to withdraw from the study at any time upon request. An investigator may terminate participation in the study if:

- An investigator determines continued participation is not in the participant's best interest.
- The study is discontinued.
- The Ottawa Health Science Network Research Ethics Board (OHSN-REB) withdraws study approval.

Handling of Participant Withdrawals or Termination

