Reminders will be distributed using the OCEAN secure messaging system integrated with the CCHC electronic medical record (EMR). The reminder will include a unique link to a landing page, where participants can select their preferred language (English, French, Arabic, or Mandarin) to view the tailored content. A schematic of the intervention experience follows, along with a copy of the landing page.

To manage clinic capacity, reminders will be distributed in two waves, each consisting of 80 (+1) participants per condition. Wave 1 participants will receive reminders on Day 1 and will be tracked for 90 days. Wave 2 participants will receive reminders on Day 30 and will be tracked for 90 days (Day 120). Control participants will be matched to these waves to ensure comparable observation periods.

ARM	Wave 1	Wave 2	TOTAL
1 (Control)	83	82	165
2 (Intervention)	83	82	165
TOTAL	166	164	330

Wave	Group	Day 1	Days 1-	Day 30	Days 30-	Day	Day	Day 121	Day 151
			29		120	90	120		
Wave	INTERVENTION	Send	Track bo	rack booking and attendance			Debrief		
1		reminder							
	CONTROL	No	Track booking and attendance				Debrief and DRS		
		reminder						reminder	
Wave	INTERVENTION			Send	Track booking and		t		Debrief
2				reminder	attendance				
	CONTROL			No Track booking and		t		Debrief and DRS	
				reminder	_				reminder

Participant Contact and Booking Process

[figure not shown]
Participants will be able to contact DESO (Diabetes Eye Screening Ottawa) at CCHC via phone, routine CCHC workflow:

- 1. DESO staff will initiate the booking process by faxing a referral to the participant's primary care provider.
- 2. Once the referral is received, the administrator will contact the participant to schedule an appointment.
- 3. If an interpreter is required, one will be arranged unless declined by the participant.

Debriefing Procedures

Debriefing procedures are as follows (and presented in the figure below):

- In-person debriefing: Participants attending a DRS appointment will receive a verbal debrief upon arrival at CCHC.
- Electronic debriefing: Participants who do not attend an appointment will receive a written debrief via the OCEAN EMR system.
- Debriefing materials will explain the study's purpose, data usage, and instructions on how participants can withdraw their data if desired.

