We will use random number generation to assign a condition (control or reminder) to a client at the CCHC. Specifically, the CCHC member responsible for data management will share a CSV file containing unique client ID codes of all eligible individuals. Then the OHRI statistician (MT, BY) will conduct the randomization schedule below, through creating a randomized list of eligible individuals in a spreadsheet containing unique participants IDs. Once the file is prepared, the statistician will lock columns in the document to prevent errors and send the locked document to the CCHC. The document will be stored in an encrypted, limited access folder on the CCHC network. The unlocked columns of the spreadsheet will be used to track whether the client responded to the reminder and other study variables (see below for example spreadsheet). When the data is sent to the OHRI post-

trial, the client ID column will be removed and replaced by "Participant 1- ..." before sharing to clear the document of direct identifiers.

RANDOMIZATION SCHEDULE

- 1) 330 participants randomly selected from all eligible individuals listed in the Community Diabetes Education Program of Ottawa (CDEPO), registered at Centretown Community Health Centre (CCHC).
- 2a) 330 eligible participants randomly assigned to control (n = 165) or intervention (n = 165)
- 2b) Participants control and intervention groups should be balanced across age and date of last chart update
- 3a) Control group randomised into wave 1 and wave 2 (n= 80; 81)
- 3b) Intervention group randomised into wave 1 and wave 2 (n= 80; 81)

Statistical Considerations

Study Hypotheses

- Linguistically tailored reminders will significantly increase DRS appointment attendance (primary outcome) compared to no reminder.
- Linguistically tailored reminders will significantly increase DRS appointment booking compared to no reminder.

Sample Size Determination

Sample size calculations are based on a minimum effect estimate of 10% (based on the effective sizes usually detected in DRS trials¹⁸) and to achieve 80% power, which requires a total sample of 250 participants. To achieve this sample size, we have estimated we will need to randomize 330

individuals registered to the CDEPO program at CCHC to account for approximately 30% attrition due to outdated contact details or death.

Statistical Methods

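### Eligibility excludes only clients already screened at DESO, checked once on Day 0, so clients with a pending booking or referral enter both arms and dilute the effect

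*Protocol*

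**What the plan says.** Inclusion criterion (f) requires that clients "have not already attended a DRS appointment with DESO", as shown in the EMR, and the Participant Exclusion Criteria mirror it. Neither list mentions a booked appointment or a referral under way.

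The randomisation schedule, under Control of Bias and Confounding, begins with "330 participants randomly selected from all eligible individuals listed in the Community Diabetes Education Program of Ottawa (CDEPO") and then assigns arm and wave. The Schematic of Study Design and the Schedule of Activities place identification, selection and randomisation on Day 0 for both waves. No eligibility check appears at Day 30.

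The Intervention Phase section states: "Wave 2 participants will receive reminders on Day 30 and will be tracked for 90 days (Day 120"). Its wave table starts wave-2 tracking on Day 30 in both arms.

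The secondary outcome is "The proportion of participants in each condition who book a DRS appointment at CCHC". The primary outcome is worded in the same way for attendance. Neither requires that the booking follow the start of the wave.

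Under Participant Contact and Booking Process, DESO first faxes a referral to the primary care provider and schedules only once the referral is received. The example tracker has a date of client contact and an in-process booking status, but no booking or attendance date. The example csv has yes/no fields only.

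**The concern.** The booking process has a built-in lag, so on any given day some clients may be between first contact and appointment. Criterion (f) lets them in. For a client already booked on Day 0, the booking outcome is met before exposure, and attendance is likely with or without the reminder. A wave-2 client who books between Day 1 and Day 29 has likewise acted before the reminder, yet attends inside the tracking window.

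A third group has no rule at all: wave-2 clients who attend on Days 1-29. They no longer fit criterion (f), and attendees are debriefed on arrival. Those in the intervention arm would nevertheless be sent the reminder on Day 30.

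What is at stake is the sensitivity of the comparison. The planned control rate is about 5 attendees among 165 (0.03 x 165 = 4.95), so a few unrelated events per arm move the relative difference noticeably. The booking outcome is the more exposed of the two, because a prior booking satisfies it outright.

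**Working it through.** **Inputs from the protocol (Total Number of Participants and Sites).**

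- Test: the calculation is made "using a two-sided Z-test with pooled variance at a 5% significance level".
- Target: "This sample size achieves 80% power to detect a 10% difference in the primary outcome".
- Planned attendance, as the section puts it: "a proportion of 0.03 in the control arm versus 0.13 in the intervention arm".
- Allocation: "Participants will be randomly allocated 1:1 to either an intervention or control arm (165 per arm").

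Sample Size Determination adds a required total of 250, i.e. 125 per arm.

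**The plan's own figure.** With p1 = 0.03, p2 = 0.13 and mean 0.08:

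n per arm = [1.96 x sqrt(2 x 0.08 x 0.92) + 0.8416 x sqrt(0.03 x 0.97 + 0.13 x 0.87)]^2 / 0.10^2 = (0.752 + 0.317)^2 / 0.01 = 114.4, so 115 per arm and 230 in total.

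Dividing by 0.70 gives 329, which agrees with the planned 330. Dividing by 0.90 gives 256. The two attrition figures in the protocol (about 10% and about 30%) differ and need reconciling separately. Because of that uncertainty, power is shown below at both 165 and 125 per arm.

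**Adding pending clients.** Let c be the share of each arm with a pending appointment who keep it. The documents give no value, so c is an assumption. If c comes on top of the planned rates:

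- control rate = c + (1 - c) x 0.03
- intervention rate = c + (1 - c) x 0.13
- power = Phi{[d x sqrt(n) - 1.96 x sqrt(2 x pbar x (1 - pbar))] / sqrt(p1(1 - p1) + p2(1 - p2))}, where d = p2 - p1 and pbar is the mean rate

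| c | Control | Intervention | Difference (points) | Ratio | Power, 165 per arm | Power, 125 per arm |
|---|---|---|---|---|---|---|
| 0 | 3.0% | 13.0% | 10.0 | 4.33 | 92.1% | 83.4% |
| 1% | 3.97% | 13.87% | 9.9 | 3.49 | 88.7% | 78.8% |
| 2% | 4.94% | 14.74% | 9.8 | 2.98 | 85.1% | 74.2% |

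In clients, c = 1-2% is 1.65 to 3.3 per arm of 165.

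**Is 1-2% a sensible range?** If bookings arrive steadily at the 3% per 90 days planned for controls, and the wait from contact to appointment is 30 days (both assumed), the pending stock on Day 0 is 3% x 30/90 = 1%. A wait of 60 days would give 2%.

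**Wave-2 attendances before Day 30.** At the same steady rate, 164 x 0.03 x 29/90 = 1.6 clients in the whole trial, or 0.8 per arm of 82.

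**The case against.** Four points on the other side carry weight.

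- **Wave-2 attendances on Days 1-29.** A reader might infer that these count as outcomes. The Intervention Phase section does not support that: tracking for wave 2 starts on Day 30 in both arms. What remains is that no rule covers these clients, and they number about 1.6.
- **Recoverability.** A reader of the example csv might infer that early cases can never be identified. That goes too far. The tracker holds a contact date, Procedures/Evaluations says all tracker information is shared, and the Data Management Plan lists date of contact among the data. A contact date before the wave start would flag many such cases. It is not a booking or attendance date, however, so it cannot apply the tracking windows exactly.
- **Attendance fixed in advance.** It is tempting to say that the reminder cannot affect a client who is already booked. The Secondary Objectives recognise that not everyone who books attends, and the tracker has a no-show option. Only booking status is settled beforehand; a reminder could still change attendance.
- **Size.** The share c is hypothetical, and the planned 3% may already include pending clients, in which case adding c overstates the loss. Shares much above 2% are hard to credit: 5% would put more clients in the queue on one day than are expected to attend in 90 days.

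It could also be said that rules on which events count belong in an analysis plan. That is fair for the counting rule, but not for the eligibility criterion or the recorded fields, which must be settled before Day 0.

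**Conclusion.** The point stands in a limited form. The stated eligibility rule admits clients with a pending DESO booking or referral, both waves are checked on Day 0 only, and neither outcome requires the booking to follow the wave start.

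A reader might infer bias, but the documents do not support it. Randomisation and wave-matched controls spread these clients evenly in expectation. The consequence is dilution, mainly of the relative difference and the booking outcome. The absolute difference hardly moves (10.0 to 9.9-9.8 points).

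With an assumed 1-2% pending, the ratio falls from 4.3 to 3.5-3.0 and power drops by about 3 to 7 points at 165 per arm, staying above 80%. At 125 per arm even 1% takes power just below 80%. These figures assume that every pending client attends in both arms and that the planned 3% excludes them; if either fails, the loss is smaller.

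**What to change.** 1. Extend criterion (f) and the matching exclusion to: *has not attended DESO, and has no DESO appointment booked or referral in process*. Clinic staff apply this as an EMR filter before the random draw.
2. Preferably draw and randomise wave 2 just before Day 30 with the same filter, so that nobody is removed after randomisation. If both waves stay randomised on Day 0, keep every wave-2 client in the analysis; dropping them later would conflict with the intention-to-treat rule in Statistical Methods. State beforehand how a booking or attendance on Days 1-29 is scored, identically in both arms.
3. Add booking and attendance dates to the tracker and the csv. The stated windows (Days 1-90 and Days 30-120) and a condition that the booking falls on or after the wave start can then be applied in the same way to both arms.

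The cost is a short amendment, a slightly smaller eligible pool, two date fields and, if wave 2 is drawn later, a second draw and a second file exchange between the clinic and the statistician.
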